### 4.1 Patients Selection and Inclusion Criteria

Acute HF expressed by acute Dyspnea New York Heart Association (NYHA) class III or IV and a BNP level  $\geq 500$  ng/l (or NTpro-BNP level  $\geq 2000$  ng/l). Due to inverse association of BNP levels and BMI, for Patients presenting with BMI of  $\geq 35$  kg/m^2, the BNP cut point is  $\geq 350$  ng/l (or NTpro-BNP level  $\geq 1400$  ng/l) (32–34). Only NTpro-BNP, but not BNP, can be used for the inclusion of patients treated with LCZ696 (“Entresto”) (35,36). The diagnosis of acute HF is additionally based on typical symptoms and clinical findings, supported by appropriate investigations such as ECG, chest X-ray, and Doppler-echocardiography as recommended by current ESC guidelines on the diagnosis and treatment of acute HF(1,2). For inclusion in this study, all of the following criteria must apply:

- Acute HF.
- Age at least 18 years.
- Informed consent.
- Negative pregnancy test (only in female patients younger than 60 years).

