On day 2 (24 h till 48h) the dosage of transdermal nitrates will be adjusted according to systolic blood pressure. In addition, at 24 hours after study inclusion, therapy with a peroral ACE-inhibitor or in case of ACE-inhibitor intolerance an ARB will be initiated. Should the patient be already on an ACE-inhibitor, the dosage remains unchanged for the first 24 hours. On day 2 (after 24 hours) the ACE-inhibitor will be up-titrated according to therapy schedule (Figure 5a) starting from day 2. Thereby, the up-titration will be performed on the top of the precedent ACE-inhibitor / ARB dosage. Should the patient be already on a maximal dosage of an ACE-inhibitor, an ARB will be added at low dose once daily and up-titrated according to the therapy schedule. In patients with chronic HF and a LVEF below 35%, the treating physician may at any time (both in-hospital and after hospitalization) consider to replace a preexisting therapy with an ACE-inhibitor or ARB with LCZ696 as recommended in the 2016 ESC guidelines (37). Should the patient already be on LCZ696 (“Entresto”), the dosage remains unchanged for the first 24 hours. On day 2 (after 24 h) the dose of LCZ696 will be up-titrated by 25% if not already on target dose (200 mg b.i.d.). Again, the dose should be increased by 25% at the end of hospitalization (if not already at 200 mg b.i.d.).

Intervention group	day 1 at hospital admission		day 1 6 h after admission		
	< 130 	> 130 	90 - 110	111 - 130	> 130
systolic blood pressure [mm Hg]	< 130 	> 130 	90 - 110	111 - 130	> 130
per oral Glyceryl trinitrate capsule (i.e. Nitroglycerin Streuli ® ) 0.8 mg  or Spray (i.e. Corangin Nitrospray ® ) 0.4mg	3 or 6 applic.	3 or 6 applic.			
transdermal Glyceryl trinitrate (i.e. Nitroderm ® TTS) [mg / 24 h]	40 - 60	60 - 80	+ 0	+ 20 - 40	+ 20 - 60
Hydralazine (i. e. Hydrapres ® ) 25 mg	1 - 1 - 1 - 1	1 - 1 - 1 - 1	1 - 1 - 1 - 1	1 - 1 - 1 - 1	1 - 1 - 1 - 1
Ramipril (i. e. Triatec ® ) [mg/d] 					
Lisinopril (i. e. Zestril ® ) [mg/d] 					
Enalapril (i. e. Reniten ® ) [mg/d] 					

-  The lowest blood pressure value measured at the emergency department before study inclusion will be considered.

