### **Study Therapy Control Group**

The current guidelines of the European Society of Cardiology do not recommend the use of ACE-inhibitors or ARB in the early stabilization of patients with acute HF (41). (37). The administration of previously prescribed ACE-inhibitors or ARB should be continued on admission with AHF, except in the presence of hemodynamic instability, hyperkalemia or severely impaired renal function. In these cases, the daily dosage of oral therapy may be reduced or stopped temporarily until the patient is stabilized. In the absence of a prescription, an initiation of the medication before discharge from hospital and up-titration every two to four weeks is recommended (37). Accordingly, patients in the control group will receive (1,2) oxygen application, treatment with diuretics based on extent of fluid overload and recent weight gain. The dosage thereby will be adjusted to renal function. Further on, after 24 to 48 hours, treatment with an ACE-inhibitor (or ARB) will be started in low dosages displayed in Figure 5b. After six to eight days of treatment, dosage of the ACE-inhibitor / ARB will be up-

titrated following the schedule displayed in Figure 5b dependent on hemodynamic and renal tolerance. As in the Intervention group, in patients with chronic HF and a LVEF below 35%, the treating physician may at any time (both in-hospital and after hospitalization) consider to replace a preexisting therapy with an ACE-inhibitor or ARB with LCZ696 as recommended in the 2016 ESC guidelines (36). Should the patient already be on LCZ696 (“Entresto”), the dosage will remain unchanged for the first 4 to 5 days with the option of increasing the dose by 25% at the end of hospitalization (if not already at 200 mg b.i.d).

Transdermal nitrates can be used, but only in the doses currently approved in Switzerland (e. g. Nitroderm TTS 5 mg / 12 h or 10 mg / 12h). The use of nitrates or hydralazine in higher doses is strongly discouraged. The use of a specific blood pressure target is up to the discretion of the treating physician.

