### **General Procedure for Both Groups**

At any time in the study the use of further treatment including loop diuretics, aldosterone antagonists, morphine or other drugs or non-pharmacological therapies (including non-invasive ventilation) will always be dependent on the clinical conditions and will be at the discretion of the treating physician.

Non-invasive hemodynamic monitoring will be performed every 10 to 30 minutes during the first hour, every 30 to 90 minutes in the second to the fourth hour, and every 6 to 8 hours for the rest of the hospitalization as currently in practice at the enrolling institutions. Continuous recording of a three-channel ECG and transdermal oxygen saturation provided by automated monitoring systems will be applied as clinically indicated.

At the time of initial presentation and before discharge the patient leg circumference will be measured at three distinct points on either side: 10 cm distal from the caput fibulae, 5 cm above the ankles and at the middle of the metatarsi. The points of measurement will be marked. A special tape measure incorporating a spring exercising constant tension will be used ensuring a measurement independent of the strain applied by the investigator. Simultaneously and when possible, the central venous pressure will be obtained with a high resolution ultrasound imaging device combined with a translucent pressure manometer.

In addition, 15 ml of serum, EDTA plasma and urine will be collected at five time points (at baseline, at day 1, day 2, day 6 and discharge) for the measurement of biomarkers such as BNP, NT-proBNP, mid-regional pro-atrial natriuretic peptide, pro-adrenomedullin, copeptin, N-GAL, Cystatin C, Troponin T, and pro-endothelin that also reflect the response to treatment. The determination of NT-proBNP, mid-regional pro-atrial natriuretic peptide, pro-adrenomedullin, copeptin, N-GAL, Cystatin C, Troponin T, and pro-endothelin and pro-endothelin will be performed collectively after hospital discharge of patients and has no effect on patient treatment.

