This trial was designed as a prospective, randomized, controlled multicenter study aimed to enroll 770 patients presenting with acute heart failure at the emergency departments at the participating study sites. Patients will be randomly assigned 1:1 after stratification for site and B-type natriuretic peptide (BNP, NT-proBNP) levels to an early goal-directed therapy or standard care according to current guidelines. Early goal-directed therapy aims to aggressive vasodilatation by using sublingual and transdermal nitrates, hydralazine (to avoid tolerance to nitrates) and rapid up-titration of angiotensin converting enzyme inhibitors and angiotensin II receptor blockers with a target systolic blood pressure of 90 mmHg to 110 mmHg. Timing and dosing of diuretics and all other treatments are left to the discretion of the treating physician in both groups. The primary endpoint is death or heart failure readmission within 180 days. Secondary endpoints include the quantitative assessment of dyspnea, need for admission to the intensive care unit, surrogate markers like BNP or NT-proBNP, the digitally recorded third heart sound, renal function, time to discharge, functional status and quality of life, falls, total treatment cost, and cost-effectiveness. Patients will receive extensive clinical and economic follow-up of at least 360 days. A clinical endpoint committee blinded to group assignment will adjudicate endpoints.

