### b. Secondary objectives

Secondary endpoints are:

- All-cause mortality at 180 days.
- HF re-hospitalization at 180 days.
- Death or re-hospitalization from all causes at 180 days.
- Need for ICU admission during initial hospitalization.
- Acute coronary syndrome during initial hospitalization.
- Symptomatic hypotension during initial hospitalization.
- B-type natriuretic peptide (BNP) and creatinine level at 48 h and at discharge.
- Changes in circumferences of both legs and central venous pressure during hospitalization.
- Change in patient-assessed dyspnea at 48 h and prior to discharge.
- Blood pressure course over the first 6 days.
- Time to disappearance of a third heart sound (if present initially).
- Time to discharge.
- In-hospital days for HF at 180 days and 360 days.
- Total treatment cost at 180 days and 360 days.
- Functional status at 180 days and 360 days.
- Quality of life (EQ-5D-3L) at 180 days and 360 days.
- Fractures due to falls within 180 days and 360 days.
- Death or HF re-hospitalization at 360 days.

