### **q. Definition of sub-group populations in different analyses**

Predefined subgroups are as follows: patients younger versus older than 75 years of age, men versus women, HF with reduced LVEF (LVEF< 40%) versus HF with mid-range LVEF (LVEF 40-49%) versus HF with preserved LVEF (LVEF≥50%), systolic blood pressure at randomization lower versus ≥120 mmHg, coronary artery disease present or not, BNP

---

 Major protocol deviations defined as the disclosure of exclusion criteria after enrollment.

concentration at randomization lower or  $\geq 1000$  pg/ml, patients with versus without known chronic heart failure, and estimated glomerular filtration rate  $< 60$  ml/min versus  $\geq 60$  ml/min.

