64 **iv. Endpoint tables**

65 The following table will be produced and

66 Table 3 will be provided in the main publication:

67

68 **Table 3: Primary and secondary endpoint events**

Event	Intervention arm (N=)	Standard of care arm (N=)	Hazard Ratio (95%CI)	p-value
Primary composite endpoint – no. (%)†	xx (xx%)	xx (xx%)	x.xx (x.xx-x.xx)	x.xx
All-cause mortality — no. (%)	xx (xx%)	xx (xx%)	x.xx (x.xx-x.xx)	x.xx
Heart failure hospitalization – no. (%)	xx (xx%)	xx (xx%)	x.xx (x.xx-x.xx)	x.xx
Secondary endpoints – no. (%)	xx (xx%)	xx (xx%)	x.xx (x.xx-x.xx)	x.xx
All-cause mortality at 180 days.— no. (%)	xx (xx%)	xx (xx%)	x.xx (x.xx-x.xx)	x.xx
Heart failure hospitalization – no. (%)	xx (xx%)	xx (xx%)	x.xx (x.xx-x.xx)	x.xx
Death or re-hospitalization at 180 days. — no. (%)	xx (xx%)	xx (xx%)	x.xx (x.xx-x.xx)	x.xx
Need for ICU admission during initial hospitalization — no. (%)	xx (xx%)	xx (xx%)	x.xx (x.xx-x.xx)	x.xx
Acute coronary syndrome during initial hospitalization — no. (%)	xx (xx%)	xx (xx%)	x.xx (x.xx-x.xx)	x.xx
Symptomatic hypotension during initial hospitalization — no. (%)	xx (xx%)	xx (xx%)	x.xx (x.xx-x.xx)	x.xx
B-type natriuretic peptide (BNP) level – ng/l (±SD)	xx±xx	xx±xx	x.xx (x.xx-x.xx)	x.xx
at 48 hours	xx±xx	xx±xx	x.xx (x.xx-x.xx)	

69

	Intervention arm				Standard of care arm				Intervention vs standard of care	
	Baseline (N=)	Follow-up (N=)	Change FU vs Baseline	p-value	Baseline (N=)	Follow-up (N=)	Change FU vs Baseline	p-value	Mean difference of the change	p-value
at discharge										
Creatinine level – µmol/l (±SD)		XX±XX			XX±XX				x.xx (x.xx-x.xx)	
at 48 hours										
at discharge		XX±XX			XX±XX				x.xx (x.xx-x.xx)	
Changes in circumferences of both legs during initial hospitalization – cm (±SD)		XX±XX			XX±XX				x.xx (x.xx-x.xx)	
Blood pressure course over the first 6 days – mmHg (±SD)		XX±XX			XX±XX				x.xx (x.xx-x.xx)	
Time to disappearance of a third heart sound (if present initially) – days (±SD)		XX±XX			XX±XX				x.xx (x.xx-x.xx)	
Quality of life assessed at 90 days (±SD)	N= xx	N= xx	N= xx	x.xx	N= xx	N= xx	N= xx	x.xx	N= xxx	
Total triAS scale – mean score (±SD)	xx±xx	xx±xx	xx±xx	x.xx	xx±xx	xx±xx	xx±xx	x.xx	xx±xx	x.xx
Fractures due to fall within 180 days and 360 days – no. (%)		xx (xx%)			xx (xx%)				x.xx (x.xx-x.xx)	
Death or HF re-hospitalization at 360 days – no. (%)		xx (xx%)			xx (xx%)				x.xx (x.xx-x.xx)	

70

71

72

73

74

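### The peptide endpoint and severity subgroup use BNP only, with no rule for patients on LCZ696 or qualified on NT-proBNP; the planned NT-proBNP assay and the randomisation stratum would close the gap

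*Combined protocol and SAP*

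**What the plan says.** **Endpoint.** Protocol 2.2 and SAP 2.2 (b) list "B-type natriuretic peptide (BNP) and creatinine level at 48 h and at discharge". The matching row in SAP Table 3 is "B-type natriuretic peptide (BNP) level", with no NT-proBNP row. The protocol summary and SAP synopsis are looser: "surrogate markers like BNP or NT-proBNP, the digitally recorded third heart sound".

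**Subgroup.** Protocol 2.2 splits patients at a BNP of 1000 pg/ml. SAP 5.7 (q) does the same, by BNP "concentration at randomization lower or" at least 1000 pg/ml.

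**Entry and randomisation.** Protocol 4.1 lets a patient qualify on either peptide, with one restriction: "Only NTpro-BNP, but not BNP, can be used for the inclusion of patients treated with LCZ696". The protocol's randomisation section and SAP 3.3 stratify on BNP around 1000 ng/l or NT-proBNP around 4000 ng/l.

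**LCZ696 in hospital.** For patients already on the drug, the intervention arm has this rule: "On day 2 (after 24 h) the dose of LCZ696 will be up-titrated by 25% if not already on target dose". In the control arm "the dosage will remain unchanged for the first 4 to 5 days". In both arms the treating physician may switch patients with chronic HF and LVEF below 35% to LCZ696 at any time.

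**Samples.** Protocol 5 (General Procedure for Both Groups) plans blood at baseline, day 1, day 2, day 6 and discharge, and names both BNP and NT-proBNP among the biomarkers. The assay of NT-proBNP and several others "will be performed collectively after hospital discharge of patients and has no effect on patient treatment". BNP is not in that batch list.

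**The concern.** The protocol treats BNP as unusable for judging entry under LCZ696, then relies on BNP at 48 h and discharge in the same patients without comment. The LCZ696 rules also differ by allocation in the window before the 48 h sample. If LCZ696 affects the BNP reading, part of any between-arm difference in BNP could come from the drug's effect on the assay and not from decongestion.

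The subgroup has a separate problem. Its cut is the BNP half of the stratification rule with the NT-proBNP half left off. A patient who qualified on NT-proBNP has no defined place unless a baseline BNP was also run. A patient on LCZ696 would be classed on the peptide that the protocol sets aside at entry.

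The SAP synopsis presents faster and larger BNP reduction as part of the main hypothesis, so readers will look at this result even though it is secondary.

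**Working it through.** The documents give no power, SD, LCZ696 share or assay share for this endpoint, so there is no planned figure to reproduce. The point rests on comparing the text; the arithmetic only shows a range.

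**1. Which peptide each part of the plan uses**

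| Use | BNP | NT-proBNP |
|---|---|---|
| Inclusion (Protocol 4.1) | yes, except on LCZ696 | yes |
| Randomisation stratum (SAP 3.3) | cut 1000 ng/l | cut 4000 ng/l |
| Endpoint list and SAP Table 3 | yes | no |
| Synopses | either | either |
| Subgroup (SAP 5.7) | cut 1000 pg/ml | no |
| Batch assay after discharge | not listed | listed |

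Since 1 pg/ml = 1 ng/l, subgroup and stratum coincide for patients stratified on BNP. They part company only for those stratified on NT-proBNP, which must include everyone on LCZ696 at entry.

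**2. Timing.** The intervention-arm dose step comes after 24 h, before the 48 h sample. The control-arm dose is held past 48 h. At discharge controls may also have had a step, while the intervention arm has further steps, so a contrast can remain. SAP Table 2 has no LCZ696 row, so a reader could not judge exposure.

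**3. Possible size at the endpoint (all inputs assumed).** Let f be the share of patients on LCZ696, equal in both arms. Let r be the between-arm ratio of the assay effect in those patients. The spurious ratio of geometric means is exp(f × ln r) = r^f.

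| f | r = 1.1 | r = 1.25 | r = 1.5 | r = 2.0 |
|---|---|---|---|---|
| 0.01 | 1.001 | 1.002 | 1.004 | 1.007 |
| 0.05 | 1.005 | 1.011 | 1.020 | 1.035 |
| 0.10 | 1.010 | 1.023 | 1.041 | 1.072 |
| 0.20 | 1.019 | 1.046 | 1.084 | 1.149 |

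If r = 1 the bias is nil. With 385 per arm and an assumed SD of log BNP of 1, the standard error is √(2/385) = 0.072. The shift in z is f × ln r / 0.072: 0.01 at f = 0.01, r = 1.1; 0.48 at f = 0.05, r = 2.0; 1.92 at f = 0.20, r = 2.0. The documents give neither f nor r, and the direction of the effect is not stated either.

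**4. Possible loss of BNP values (share m assumed).** With n = 385 × (1 − m) per arm, the ratio detectable with 80% power is exp[(1.960 + 0.842) × √(2/n)], again with SD 1.

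- m = 0: 770 patients, ratio 1.22
- m = 0.10: 693 patients, ratio 1.24
- m = 0.25: about 578 patients, ratio 1.26
- m = 0.50: 385 patients, ratio 1.33

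**5. Whether the remedy is already in the plan.** NT-proBNP is a planned assay on study samples. SAP 6.1 stratifies the Cox model by the randomisation factor, so the stratum must already be in the analysis file. One gap remains: the SAP 3.5 (h) schedule shows blood and urine collection on D1, D2, D3 and D6 and nothing in the discharge column, against the protocol's discharge sample.

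**The case against.** The strongest reply is that the protocol restricts BNP for inclusion only. Nothing in the documents says that LCZ696 alters BNP on treatment, or by how much. Extending the restriction to the endpoint is a reasonable inference, but it is an inference.

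The contrast is also limited. Existing users continue the drug in both arms, new starts are allowed in both, and the protocol-driven difference at 48 h is one 25% step in users below target. Large values of r would need something near full drug effect in one arm and none in the other, which is not the design. Recruitment began in November 2007, and the option to switch to LCZ696 is tied to a 2016 guideline, so the overall share may be small. All of this stands, and it is why no size is claimed.

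A reader might infer that everyone enrolled on NT-proBNP drops out of the subgroup. At an assumed 20% to 50% that would be 0.2 × 770 = 154 to 0.5 × 770 = 385 patients. The documents do not support this: the protocol plans BNP on baseline samples too. The risk is narrower, namely missing BNP where a site runs only NT-proBNP, since BNP is outside the batch list.

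The plan also has partial cover. The synopses allow either peptide, further biomarkers are to be tabulated, and missing secondary values are imputed in sensitivity analyses (SAP 6.5, 10.1.5). But the synopses conflict with the endpoint list. Imputation does not address a BNP value that is present but affected by the drug, and no text says that NT-proBNP would inform a missing BNP.

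Finally, log-scale adjusted analysis is a separate choice from the choice of peptide. That is true. It is offered because SAP 10.2.3 otherwise gives an unadjusted Mann–Whitney test.

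**Conclusion.** The gap is real: a BNP-only endpoint and a BNP-only subgroup, with no rule for LCZ696 users or for patients with NT-proBNP alone. The endpoint is exposed to an arm-dependent assay effect and the subgroup to lost or misclassified patients.

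A reader might go further and conclude that both results are distorted. The documents do not show that, because the LCZ696 share and the assay effect are not given. The illustrated ratios of 1.001 to 1.149 rest wholly on assumed f of 1% to 20% and r of 1.1 to 2.0, and the true bias may be negligible. Nor does the subgroup problem bias the randomised comparison within a subgroup, since the classifying value is taken at baseline.

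The primary endpoint and the sample size are untouched, and SAP 6.6.4 makes all secondary analyses exploratory. The change is worth making because it costs little and removes a later choice between two peptides.

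**What to change.** 1. In SAP 5.7, define the severity subgroup as the randomisation stratum: BNP below or above 1000 ng/l, or NT-proBNP below or above 4000 ng/l.
2. In SAP 2.2 and Table 3, add NT-proBNP at 48 h and discharge, alongside or in place of BNP. Analyse it in all randomised patients whatever their LCZ696 use, on the log scale with baseline log NT-proBNP as covariate, and report a ratio of geometric means.
3. If a supportive BNP analysis leaves out LCZ696 users, exclude on baseline use only. Later use is a physician's decision in an open-label trial, and excluding on it would give up the protection of randomisation.
4. Reconcile the discharge sample between Protocol 5 and the SAP assessment schedule. Make the endpoint list and the two synopses name the same peptide.

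The cost is SAP wording and one table row. NT-proBNP is already a planned assay and the stratum already exists. The one dependency is the discharge sample: if it was not collected, the discharge part of the endpoint is at risk for either peptide.

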### **c. Assessment of objectives**

Overall, the endpoints are assessed during the initial hospitalization and the follow up period. The patients are contacted after 90, 180 and 360 days by telephone calls or in written form. The family physicians are called if these individuals could not be contacted. Information is furthermore obtained by institutional chart review and the national registry on mortality.

The primary endpoints will be adjudicated by a clinical endpoint committee blinded to group assignment and using all the information available corresponding to the event.

Additional, for the assessment of the secondary endpoints, all the events occurring during the initial hospitalization, leg edema and vital signs measurements are collected.

### **d. Changes of the primary objective during the conduct of the study**

No changes in the primary objective occurred during the conduct of the study.

## **3. Study design**

### **e. General design and plan**

This trial is designed as an open label, prospective, randomized, controlled multicenter study.

### **f. Sample size**

Sample size calculation is based on the on the data from the BASEL V study. A hypothesized 20%-decrease of the composite endpoint death or HF re-hospitalization at 180 days, will require 385 patients per treatment arm to obtain, with a probability of 80%, a log rank test result that is statistically significant at the 5%-level. In order to compensate for an expected 1-2% of patients in whom the primary endpoint could not be assessed at 180 days due to loss to follow-up or complete withdrawal of ICF, it was planned to enroll approximately 780 patients.

